The collection status of the intake survey should be recorded in the tracking system. This is done by completing the “[Visit 1-Collect Info about Intake Completion](#)” task in the tracking system. Detailed information on completing this task can be found in the “[Tracking System Tasks](#)” section on page 104. Additionally, if the intake survey is *not* collected during the clinic visit, a note should be made (using the [Notes](#) tab in the participant’s tracking system page (see page 72) that includes information about whether the intake survey was completed or not prior to the visit.

¹ When possible the SC will contact the RA via text or phone, to remind them to check with the provider/genetic counselor to learn if the participant will be seen and if so, can the pre-visit survey occur.

Additional Notes on Document Collection

The task “Questionnaires-Collection Method” allows for tracking the type of questionnaire collection for the Baseline/Intake, Pre-visit Parent, Post-visit Parent, and Post-Visit Clinician surveys. This task should be completed by the RA but may be completed by other study staff members. The RA or staff member will note if the questionnaire was completed by phone, on the tablet, or by paper. For details on completing this task, see the “[Tracking System Tasks](#)” section on page 145.

Parent attempts to give RA QPL? The parent has been provided with instructions to give their question prompt list (QPL) (“Visiting a pediatric specialist: It’s OK to ask questions.”) to their child’s physician. If the parent tries to hand the QPL to the RA, the RA should inform them to give the QPL to their child’s physician. If this happens, the RA may say the following: “You may ask anyone on your child’s medical team these questions, but *please make sure to give this list to the doctor.*”

Pre-visit Survey

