2. **Usual care** – Providers should *not* adjust their plan of care for a participant based on their participation in NCGENES 2 or their randomization. Providers should complete and return the results of any non-NCGENES 2 diagnostic tests according to their usual practices and timelines.
3. **Pre-RoR Mailing** – All participants will receive a “Pre-RoR” mailing of some type. The contents and timing of that mailing depend and the participant’s randomization. See below for more detail.
4. **Post-RoR Provider Survey(s)** – Providers will be asked to complete a 2-part post-RoR questionnaire for each NCGENES 2 participant. The content and timing of these questionnaires depends upon the randomization and documented treatment of the participant.
 - a. *Part 1* addresses the utility of diagnostic tests (including genome sequencing, if applicable) and plan for continued care of the patient. The participant’s primary genetic/neurology provider, usually a physician, will always complete this part of the survey.
 - b. *Part 2* addresses the actual process of returning results, i.e. the interaction with the participant’s caregiver(s). Whoever completes part 1 of the survey for a participant will indicate all parties that took part in returning results, e.g. genetic counselors or nurses. Each of those participating providers will complete a copy of part 2 of the survey for that participant.
5. **Post-RoR Parent/Caregiver Survey(s)** – Parent participants will be asked to complete a post-RoR questionnaire 2 weeks and 6 months after results have been returned. The content and exact timing of these questionnaires depends upon the randomization, documented treatment, and age of the participant. Questionnaires will be mailed to participants, but may also be completed by phone on request.

¹ This group also includes participants who are randomized to genome sequencing, but decline to receive it.

RoR for No GS Participants

The Return of Results process for No GS participants is generally simpler than that for GS participants. That being said, certain limitation of this clinical trial do create quirks that may be confusing to staff, providers, and participants.

Defining Results for No GS

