Providers of No GS participants will receive an email notification (Fig. 1) exactly 5.5 months after visit one that informs them a Post-RoR survey is due. Providers can access this survey using the link in the email or from the MD surveys tab in their tracking system account. Once Part 1 of the provider survey is complete, Part 2 will be triggered automatically. If the initial provider is completing Part 2 of the survey, they will be automatically directed to it upon completion of Part 1. Any other provider designated to complete Part 2 will receive an email notification. Surveys should be completed as quickly as possible to minimize recall bias.

Parent Post-RoR Surveys – No GS

Each parent will be sent two surveys after the RoR Date. These surveys will be mailed to the parents, filled out, and returned. Parent's also have the option of completing surveys by phone.

Post-RoR 2 Week Parent Survey

The first parent survey should be completed roughly two weeks after the RoR date. The window for completing the Post-RoR 2 week Parent survey is 0-6 weeks after return of results. For No GS participants, this means the 2 week survey should be completed between 6-7.5 months after Visit 1. Exactly six months after Visit 1, study staff will mail a survey to parents of participants not randomized to GS. For more details on this mailing, see [Mailing 4](#) in the mailings section. Staff should complete the “Post-RoR - Parent 2 Week Questionnaire Mailing” task in the tracking system upon completion of this mailing. When the parent returns a completed Post-RoR 2 week survey by mail, staff should complete the “Post-RoR - Parent 2 Week Questionnaire Mailing - Received” task in the tracking system, the paper copy of the survey should be scanned and uploaded in the participants documents, and the data in the survey should be entered in the “Post-RoR – Parent 2 Week Questionnaire” task in the tracking system. This data entry should be done regardless of whether the survey was completed within the given window. Finally, staff should send a thank you note with gift card to the parent (See [Mailing 5](#)).

Post-RoR 6 Month Parent Survey

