\$70 cash after Visit 1 (\$10 parking, \$30 intake qx, \$30 visit 1 qxs)

\$30 gift card after completion of the 2 weeks post RoR Qx by phone

In rare cases a parent will come in for a Visit 2/RoR and will be given \$40 in cash to cover \$10 parking and \$30 post visit 2/RoR questionnaire delivered at the time of the in-person visit

\$60 gift card after completion of the 6 month post RoR questionnaire by phone

TOTAL REIMBURSEMENT USUALLY \$160, in rare cases \$170 if in-person Visit 2/RoR

This section explains how compensation is acquired and tracked by NCGENES study staff.

Requesting Cash and Gift Cards at UNC

1. Staff should request 2 weeks before a need cash advance.
2. Once a cash advance is deposited to the clinical director's personal checking account (auto-deposit), another cash advance should be immediately initiated. Up to 2 cash advances may be outstanding when submitting new cash advance requests.
3. To complete a cash advance request, ask for the cash advance request form from [name], tell him the amount needed, receive via email, print, sign and return the originally signed doc to [name] (no scanned docs). [name] will get [name]'s co-signature.
4. Receipt the distribution of money by ID#, date, amount with participants' signature. This is done in the tracking system (receipt book used if tracking system does not work). The tracking system will create a printable spreadsheet of current charges (date to date) that I can be signed and given to [name] to justify each cash advance.
5. Study cash must be spent within 60 days, otherwise staff will need to provide justification of unspent money (e.g., participant no shows etc.)

Gift cards will be purchased with cash requested following the protocol above.

Purchasing Gift Cards for Mission Participants

Gift cards will be purchased by a Mission study team member and maintained in a locked box until needed.

Requesting Child Nonmonetary Gifts at UNC

The study coordinator will:

1. Request the P-Card from [name], NCGENES 2 Project Manager to make gift purchases
2. Purchase gifts and make two copies of the receipt
3. Submit the original receipt to [name]
4. Keep an Excel spreadsheet that tracks the distribution of each purchased item

5. Submit the tracking spreadsheet to [name] along with one copy of the corresponding receipt, when all of the items on a receipt have been distributed
6. Keep one copy of the receipt for the NCGENES team records

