If bus: Once you walk in the door of the Children's Hospital, the Information Desk will be right in front of you. They will help you find the Pediatric clinic where your child will see the doctor.

If Medicaid van: If you take the Medicaid van, they will pick you and your child up from your home and drop you off at the front door of the UNC Children's Hospital. Once you walk in the door of the Children's Hospital, the Information Desk will be right in front of you. They will help you find the Pediatric clinic where your child will see the doctor.

Finally, your NCGENES research appointment is scheduled for 11:15 AM. This is 45 minutes before your visit with [name], MD. That will give us time to go over the survey you did at home and for you to do the first clinic survey.

Don't forget, after the doctor visit is over, you will need to stay up to 45 minutes longer to do a survey and to talk about the second part of NCGENES that includes the possibility of getting the research genetic test.

Just to help you prepare, sometimes specialty doctor visits can take longer than expected. The total time to complete the research visit activities plus the doctor visit could mean that you and your child are at the hospital for up to 3 hours that day. Remember the other parts of study participation are much shorter, requiring only 30-minute phone interviews.

That's all the information that I have for you today. If you have any last questions, I'm happy to answer them now. [\(Pause and let them ask questions\)](#)

If you think of any questions later, please feel free to contact [name] at [contact]. Thank you very much for your time, patience and willingness to participate in this study. Have a great day/afternoon/evening!

Visit 1 Appointment Packet – with(out) Pre-Visit Prep

The “Visit 1 Appointment Packet – with(out) Pre-Visit Prep” task is a mailing task. This (and all) mailing task(s) can be started from the homepage (Fig. 1) or individual participant page (Fig. 2) by clicking the “Get Started” button for the appropriate participant.

09/05/2019 Fig. 1	Visit 1 Appointment Packet - with Pre Visit Prep (2879)			 Get Started
6 Fig. 2	09/05/2019	Visit 1 Appointment Packet - with Pre Visit Prep (2879)	Pending	 Get Started

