Research sequencing confirmation is conducted via Sanger sequencing in the UNC MGL CLIA lab (protocol available in the Appendix). CLIA confirmed results are placed in the patient's medical record which automatically notifies the UNC ordering physician. If the CLIA confirmation is being conducted for an ECU or Mission study participant, then the CLIA lab results will be sent via fax to the ordering physician. Negative research GS results are NOT confirmed in the CLIA clinical lab. Negative results notification is done by the NCGENES 2 Patient Tracking System that generates an email notification to the ordering physician indicating results are available. This notification includes a patient friendly research result report and points the MD to the molecular analysis tab to see the negative result report and requests the physician to complete the physician post-RoR survey. All results (positive, negative or uncertain) are reported to the family by the clinical genetic counselor or ordering physician by phone or in-person.

Sample reporting of NEGATIVE RESULTS by UNC NON-CLIA RENCI System - All Sites

Return of NEGATIVE RESEARCH results to NCGENES 2 patients (All Sites)

Negative research results cannot be confirmed, thus negative results will not be confirmed by either UNC CLIA Molecular Genetics Labs.

Instead negative results notification is done by the NCGENES 2 Patient Tracking System that generates an email notification to the ordering physician indicating results are available. This notification includes a patient friendly research result report and points the MD to the molecular analysis tab to see the negative result report and requests the physician to complete the physician post-RoR survey. All results (positive, negative or uncertain) are reported to the family by the clinical genetic counselor or ordering physician by phone or in-person.

Final Genomic Sequencing Report to Parent/Caregiver

At the end of the study, after the final 12-month telephone survey, parents will be mailed a final thank you letter for their participation (a copy of the final genomic sequencing results for their records MAY accompany their thank you note).

APPENDICES

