4. We are looking at medical records and insurance information for items around why they came to clinic today. That when we use this information to report on study findings, we report in generalities, like for example we saw 850 families and from 50 we learned X and from 150 we learned Y. Also mention that we place information in public databases, which is something that researchers do to learn from each other, but this information is included without any personal information on study participants.
5. Participation will not involve an additional trip to UNC, we understand that no one lives close, so the study was designed in such away as to not have them make a trip to UNC only for the study. Which is why we try to have study activities done when they are already coming.
6. What will happen today is, if they are assigned to have testing and they decide to do so, that for their child participation means giving a little extra blood today. For them it means doing a phone interview about 6-8 months from today and then another phone interview about 6-months after that. If they are assigned to no GS or decide not to have testing, then there are no activities for their child, but that they will still have the phone interviews.
7. The study's funder is part of the NIH (the part of government that funds most research).
8. The IRB is the Institutional Review Board, which is the organization that approved us to do this study and that they make sure researchers do what they say they will do. If they do not think this has occurred, they can contact the IRB with or without giving their name to discuss the issue.
9. The IRB's number is included in the consent, and that they will get a paper copy of the consent after signing.
10. The IRB requires that we have information in the consent about future use of the data, so this section discusses this use and that they can still be in the study regardless of if they decide to have or not have their information stored in the separate database.
11. Discuss the future use section of the consent and offer to let the parent read it on the screen.

12. At the end of reviewing consent form, inform the parent that in by signing this form they are agreeing to allow us to
 - 1) flip the coin to see if they are or are not offered GS testing
 - 2) to look at their child's medical and insurance information regarding information around why they came to clinic today, until their child is 18

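### Parents are told that post-result follow-up is by phone interview, but the procedure mails a paper survey, takes phone answers only on request and describes no contact with non-responders

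*Protocol*

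**What the plan says.** **What parents are told.** Appendix IV, Consent form 1, item 6, describes follow-up for families who have sequencing: "For them it means doing a phone interview about 6-8 months from today and then another phone interview about 6-months after that". For families assigned to no sequencing, or who decline it, the same item says "but that they will still have the phone interviews". The talking points for the second consent form repeat that phone interviews take place. The enrolment call script says "Remember the other parts of study participation are much shorter, requiring only 30-minute phone interviews". The section Phone Consent to Intervention 2 also describes the remaining participation as phone interviews.

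**What the payment and closing text assume.** The Parent Reimbursement list ties the last payment to a "gift card after completion of the 6 month post RoR questionnaire by phone" and words the 2-week payment the same way. The section Final Genomic Sequencing Report to Parent/Caregiver says that "after the final 12-month telephone survey, parents will be mailed a final thank you letter for their participation".

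**What staff are to do.** Return of Results, After Visit 1, item 5: "Questionnaires will be mailed to participants, but may also be completed by phone on request". The Parent Post-RoR Surveys sections for both arms say "These surveys will be mailed to the parents, filled out, and returned", with phone as the parent's option. The tasks attached to each survey, and Mailings 4 to 7, are: mail the form, log its receipt, scan and enter it, and send the gift card.

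**The concern.** The two accounts of follow-up cannot both be right, and the one given to parents is not the one that staff carry out. A parent who expects to be rung has a reason to set the form aside, and nothing in the described procedure then reaches that parent.

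The 2-week and 6-month surveys hold the parent-reported measurements after results, including the GAD7 and PHQ8. Under the Alert Protocol those scales are scored only when responses are entered, so an unreturned form also leaves that screen undone. Elsewhere the protocol does fix contact attempts: up to five enrolment calls, one or two reminder calls before Visit 1, and at least three attempts after a distress alert. The two post-result surveys have no equivalent.

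Apart from data loss, describing participation wrongly during the consent discussion should be corrected for its own sake.

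**Working it through.** **Step 1. Every statement of follow-up mode, side by side.**

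| Place in the Protocol | Mode stated |
|---|---|
| Appendix IV, Consent form 1, item 6 (both arms) | phone interviews |
| Appendix IV, Informed consent 2, item 5 | phone interviews |
| Enrolment call script | 30-minute phone interviews |
| Phone Consent to Intervention 2 | phone interviews |
| Parent Reimbursement | completion by phone, both surveys |
| Final Genomic Sequencing Report | telephone survey |
| Visit 1, Study Intervention 2 (in-clinic narrative) | surveys, mode not given |
| Return of Results, item 5 | mailed; phone on request |
| Parent Post-RoR Surveys, No GS and GS | mailed; phone optional |
| Mailings 4 and 6 | paper form with cover letter and return envelope |

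The in-clinic and phone-consent routes give the same explanation to equivalent families, yet one says surveys and the other says phone interviews. None of the listed tasks schedules an outgoing survey call or a reminder.

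**Step 2. Promised timing against the survey windows (No GS arm, months after Visit 1).**

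- The No GS RoR date is fixed at 6 months.
- 2-week survey: window 0-6 weeks after RoR, which the protocol gives as 6-7.5 months. Six weeks is 6/4.345 = 1.4 months, so 7.5 is a rounding; I use the protocol's figure.
- 6-month survey: 6 + 5 = 11 to 6 + 7 = 13 months, as the protocol states. The form is mailed at 11 months.
- Scripted first contact: 6 to 8 months. Scripted second contact: 6 + 6 = 12 to 8 + 6 = 14 months.
- Late end of the first: 8 - 7.5 = 0.5 month after the window closes.
- Late end of the second: 14 - 13 = 1 month after the window closes.

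The early ends (6 and 12 months) fall inside the windows. A No GS parent who waits until the late end of the promised period is out of window at both surveys. GS windows run from a variable RoR date, so the same check cannot be made from Visit 1.

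**Step 3. Possible size.** The protocol gives no response rate, so this is an assumed range. Let f be the share of parents who would otherwise respond but are lost because they wait. With loss at random and equal across arms, the standard error grows by 1/sqrt(1 - f). The counts use the 800 of the overview diagram (planned enrolment is 850) and assume that all would otherwise respond.

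| f | Parents of 800 | SE multiplied by |
|---|---|---|
| 2% | 16 | 1.01 |
| 5% | 40 | 1.03 |
| 10% | 80 | 1.05 |
| 20% | 160 | 1.12 |

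The counts are upper values, because no-shows, refusals and investigator withdrawals come before the second randomization.

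**The case against.** **Parents get other signals.** Mailing 3 sends every family in the second randomization a letter saying that a survey will follow. Each survey has a cover letter and return envelope, and the thank-you note after the first says that the next step is another survey. In the enrolment call parents agree to complete mailed papers and five surveys. Returns outside the window are still entered and paid. All of this stands, and it lowers the risk. None of it, as described, withdraws the promised call, and the consent talk comes after the enrolment wording.

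**Some text cannot be seen.** Appendix IV gives coordinator talking points. The consent form itself is not shown here and the enrolment script is abridged. The step-by-step guide stops at empty Pre-RoR headings and the calendaring section is unwritten, so a reminder step may exist elsewhere. That limits the point to what the protocol describes.

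**Readings that go further than the text.**

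- A reader might infer that a waiting parent leaves no post-result outcome. Provider post-RoR surveys and medical-record follow-up do not depend on the parent's form.
- A reader might infer that the loss differs by arm, since GS mailing follows a confirmed result date and No GS mailing a fixed one. Both arms hear the same script and no response data exist, so this is conjecture.
- A reader might take the 12-month label in the closing section as a contradiction. On the Visit 1 clock the No GS window is 11-13 months, so the label fits; it only lacks an anchor.
- A reader might infer that completion mode is lost, because the Collection Method task "allows for tracking the type of questionnaire collection for the Baseline/Intake, Pre-visit Parent, Post-visit Parent, and Post-Visit Clinician surveys" and no others. Paper returns have their own receipt task and are scanned, and calls are logged, so mode is largely recoverable.

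**Conclusion.** The contradiction holds. Participant-facing, payment and closing text describe two phone interviews. The working procedure mails paper forms, accepts phone answers on request, and describes no contact with parents who do not reply. The consequence is a risk of missing or out-of-window parent-reported outcomes, including the distress scales, and not a total loss of post-result data.

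The part that can be sized from the document is timing in the No GS arm: overruns of 0.5 and 1 month at the late end of the promised periods. The number of parents affected is unknown. The 2-20% range is an assumption, and the standard-error factors of 1.01 to 1.12 cover lost precision only. No bias between arms is shown. The change is worth making because the error is plain and the correction is cheap.

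**What to change.** 1. Use one statement in the enrolment script, the Appendix IV consent talking points, Phone Consent to Intervention 2, Parent Reimbursement and the closing section. It should say that a survey will be mailed, that it may be done by phone, and that the gift card is paid either way. Mailings 5 and 7 already pay on return of the form, so only the reimbursement wording needs to change. Give each timing with its anchor, Visit 1 or the RoR date.
2. Add one call to parents whose form is not back, offering phone completion inside the existing window. For example, call about 3 weeks after the 2-week mailing (the window closes 6 weeks after RoR) and about 6 months after the RoR date (mailed at 5 months, closing at 7). For GS families whose RoR date is confirmed late, check that the first call still falls inside the window.
3. Optionally, add both post-RoR surveys to the Questionnaires – Collection Method task, so that mode is a data field and need not be reconstructed.

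The cost is wording edits, one tracking item and some time from existing staff, for whom Appendix XLI already gives interviewing guidance. The downside is a larger share of phone answers. The research assistant is unblinded to the second intervention, and the 2-week form itself differs by sequencing status, so whoever takes those answers will usually know it.
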